8.4.1. Time period and frequency for collecting AEs and SAEs

All SAEs will be collected from the signing of the ICF until the final follow up visit. All AEs will be collected from the start of study intervention until the final follow up visit.

Medical occurrences that begin before the start of study intervention but after obtaining informed consent will be recorded as medical history/current medical conditions, not as AEs.

All SAEs/pregnancies will be recorded and reported to the sponsor or designee immediately and under no circumstance should this exceed 24 hours, as indicated in Section [10.3](#). The investigator will submit any updated SAE data to the sponsor within 24 hours of it being available

A poststudy AE/SAE is defined as any event that occurs outside of the AE/SAE reporting period defined in Section 8.4.1.

Investigators are not obligated to actively seek information on AEs or SAEs after conclusion of the study participation. However, if the investigator learns of any SAE, including a death, after a participant has been discharged from the study, the investigator must record it in the medical records. If the investigator considers the event to be reasonably related to the study intervention or study participation, the investigator must promptly notify the sponsor.

Contacts for SAE reporting can be found in Section 8.4.8.

8.4.2. Method of detecting AEs and SAEs

Care will be taken not to introduce bias when detecting AEs and SAEs. Open-ended and nonleading verbal questioning of the participant is the preferred method to inquire about AE occurrences.

8.4.3. Follow-up of AEs and SAEs

After the initial AE/SAE report, the investigator is required to proactively follow each participant at subsequent visits/contacts. All SAEs will be followed until resolution, stabilization, the event is otherwise explained, or the participant is lost to follow-up (as defined in Section 7.3). Further information on follow-up procedures is provided in Section 10.3.6.5.

8.4.4. Regulatory reporting requirements for SAEs

- Prompt notification by the investigator to the sponsor of an SAE is essential so that legal obligations and ethical responsibilities toward the safety of participants and the safety of a study intervention under clinical investigation are met. See Section 8.4.1 for reporting timeframes.
- For SAEs the investigator must always provide an assessment of causality at the time of the initial report, as defined in Section 10.3.6.6.
- An investigator who receives an investigator safety report describing an SAE or other specific safety information (e.g., summary or listing of SAEs) from the sponsor will review and then file it along with the CIBs and will notify the IRB/IEC, if appropriate according to local requirements.
- Investigator safety reports must be prepared for SUSARs according to local regulatory requirements and sponsor policy and forwarded to investigators as necessary.

8.4.5. Pregnancy

To be eligible to participate in the study, participants who were female at birth must not be pregnant (i.e., must have a negative pregnancy test) nor breastfeeding. In addition,

POCBP must be using acceptable forms of birth control from Screening through to Day 39. The investigator is responsible for review of medical history, menstrual history, and recent sexual activity to decrease the risk for inclusion of a POCBP with an early undetected pregnancy. Study intervention may only be administered if the screening pregnancy test (blood) and an additional pregnancy test on Day 1 (urine) are negative. Pregnancy testing for POCBP must be performed post baseline as per the SoA (Section 1.3).

- Details of all pregnancies in female participants and female partners of male participants will be collected after the start of study intervention and until Day 39.
- If a pregnancy is reported, the investigator will record pregnancy information on the appropriate form and submit it to the sponsor within 24 hours of learning of the female participant or female partner of male participant (after obtaining the necessary signed informed consent from the female partner) pregnancy.
- Any pregnancy complication or elective termination of a pregnancy for medical reasons will be reported as an AE or SAE.
- Abnormal pregnancy outcomes (e.g., spontaneous abortion, fetal death, stillbirth, congenital anomalies, ectopic pregnancy) are considered SAEs and will be reported as such.
- The participant/pregnant female partner will be followed to determine the outcome of the pregnancy. The investigator will collect follow-up information on the participant/pregnant female partner and the neonate and the information will be forwarded to the sponsor. See Section 8.4.1 for reporting timeframes.
- Any poststudy pregnancy-related SAE considered reasonably related to the study intervention by the investigator will be reported to the sponsor as described in Section 8.4.4. While the investigator is not obligated to actively seek this information in former study participants/pregnant female partner, he or she may learn of an SAE through spontaneous reporting.
- Participants who become pregnant after administration of the first study intervention dose must not receive subsequent doses of the study intervention but may continue other study procedures at the discretion of the investigator.

8.4.6. CV and death events

For any CV events detailed in Section 10.3 and all deaths, whether or not they are considered SAEs, specific CV and Death sections of the eCRF will be required to be completed. These sections include questions regarding CV (including sudden cardiac death) and non-CV death.

The CV eCRFs are presented as queries in response to reporting of certain CV MedDRA terms. The CV information should be recorded in the specific CV section of the eCRF within one week of receipt of a CV Event data query prompting its completion.

The Death eCRF is provided immediately after the occurrence or outcome of death is reported. Initial and follow-up reports regarding death must be completed within one week of when the death is reported.

8.4.7. Disease-related events and/or disease-related outcomes not qualifying as AEs or SAEs

The events or outcomes listed in the CDC Classification System for HIV-1 Infections (Section 10.8) will be recorded on the HIV-Associated Conditions eCRF page if they occur. However, these individual events or outcomes, as well as any sign, symptom, diagnosis, illness, and/or clinical laboratory abnormality that can be linked to any of these events or outcomes are not reported to VH/GSK as AEs and SAEs even though such event or outcome may meet the definition of an AE or SAE, **unless the following conditions apply:**

- The investigator determines that the event or outcome qualifies as an SAE under part 'f' of the SAE definition [Section 10.3.2], or
- The event or outcome is in the investigator's opinion of greater intensity, frequency or duration than expected for the individual participant, or
- The investigator considers that there is a reasonable possibility that the event was related to study intervention.
- Death occurring for any reason during a study, including death due to a disease-related event, will always be reported promptly, or
- Lymphomas and invasive cervical carcinomas are excluded from this exemption; they must be reported as SAEs even if they are considered to be HIV-related.

If any of the above conditions are met then record the Disease Related Event on the SAE page rather than the HIV Associated Conditions eCRF.

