10.3.2. Definition of SAE

An SAE is defined as any untoward medical occurrence that, at any dose, meets one or more of the criteria listed:

a. Results in death

b. Is life threatening

The term 'life-threatening' in the definition of 'serious' refers to an event in which the participant was at risk of death at the time of the event. It does not refer to an event, which hypothetically might have caused death, if it were more severe.

c. Requires inpatient hospitalization or prolongation of existing hospitalization

- In general, hospitalization signifies that the participant has been admitted (usually involving at least an overnight stay) at the hospital or emergency ward for observation and/or treatment that would not have been appropriate in the physician's office or outpatient setting. Complications that occur during hospitalization are AE. If a complication prolongs hospitalization or fulfills any

other serious criteria, the event is serious. When in doubt as to whether “hospitalization” occurred or was necessary, the AE should be considered serious.

 • Hospitalization for elective treatment of a pre-existing condition that did not worsen from baseline is not considered an AE.

 d. Results in persistent or significant disability/incapacity 
 • The term disability means a substantial disruption of a person’s ability to conduct normal life functions. • This definition is not intended to include experiences of relatively minor medical significance such as uncomplicated headache, nausea, vomiting, diarrhea, influenza, and accidental trauma (e.g., sprained ankle) that may interfere with or prevent everyday life functions but do not constitute a substantial disruption.

 e. Is a congenital anomaly/birth defect in the offspring of a study participant

 f. Abnormal pregnancy outcomes (e.g., spontaneous abortion, fetal death, stillbirth, congenital anomalies, ectopic pregnancy)

 g. Is a suspected transmission of any infectious agent via an authorized medicinal product

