
 h. Other situations: 
 • Possible Hy’s Law case: ALT \geq 3x ULN AND total bilirubin \geq 2x ULN ($>35\%$ direct bilirubin) or INR >1.5 must be reported as SAE • Medical or scientific judgment should be exercised by the investigator in deciding whether SAE reporting is appropriate in other situations such as significant medical events that may jeopardize the participant or may require medical or surgical intervention to prevent one of the other outcomes listed in the above definition. These events should usually be considered serious. 
 ○ Examples of such events include invasive or malignant cancers, intensive treatment for allergic bronchospasm, blood dyscrasias, convulsions, or development of intervention dependency or intervention abuse.

10.3.3. Unsolicited AE.

 • Definition of unsolicited AE

 • An unsolicited AE is an AE that was not solicited using a participant diary and that is communicated by a participant who has signed the informed consent. Unsolicited AEs include serious and nonserious AEs.

 • Potential unsolicited AEs may be medically attended (i.e., symptoms or illnesses requiring a hospitalization, emergency room visit, or visit to/by a healthcare provider). The participants will be instructed to contact the site as soon as possible to report medically attended event(s), as well as any events that, though not medically attended, are of participant concern. Detailed information about reported unsolicited AEs will be collected by qualified site personnel and documented in the participant’s records.

- Unsolicited AEs that are not medically attended nor perceived as a concern by the participant will be collected during an interview with the participants and by review of available medical records at the next visit.
- As AEs will not be solicited in this study, no list of solicited events is specified in this protocol.

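### Protocol 8.4.7 returns HIV-related events to SAE reporting through an SAE criterion that covers only pregnancy outcomes, and 10.3.1 repeats two of its five conditions with a wrong pointer

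*Protocol*

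**What the plan says.** **Protocol 8.4.7** exempts the CDC-classified HIV events of Section 10.8 from AE and SAE reporting. The exemption also covers "any sign, symptom, diagnosis, illness, and/or clinical laboratory abnormality that can be linked to any of these events or outcomes", and it applies "even though such event or outcome may meet the definition of an AE or SAE". Five conditions, any one of which is enough, move the event from the HIV-Associated Conditions page to the SAE page. The first is: "The investigator determines that the event or outcome qualifies as an SAE under part 'f' of the SAE definition". The last is: "Lymphomas and invasive cervical carcinomas are excluded from this exemption; they must be reported as SAEs even if they are considered to be HIV-related".

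**Protocol 10.3.2** letters the SAE criteria a to h. Part f reads: "Abnormal pregnancy outcomes (e.g., spontaneous abortion, fetal death, stillbirth, congenital anomalies, ectopic pregnancy". Part c reads: "Requires inpatient hospitalization or prolongation of existing hospitalization". Part h, for other situations, contains the judgement item: "Medical or scientific judgment should be exercised by the investigator in deciding whether SAE reporting is appropriate in other situations". Part h also requires possible Hy's Law cases to be reported as SAEs.

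**Protocol 8.4.5** says separately that abnormal pregnancy outcomes "are considered SAEs and will be reported as such".

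**Protocol 10.3.1** places disease-related events among those that do not meet the AE definition. It calls for prompt SAE reporting if either of two conditions applies: the event is worse than expected for that participant, or it is possibly related to study intervention. For more it refers to Section 8.4.9, which describes the participant card.

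**The concern.** The first condition in 8.4.7 should let a seriousness criterion override the disease-event exemption. As lettered, it invokes a criterion about pregnancy in a section about opportunistic infections and HIV-related cancers. An investigator who follows it exactly finds that it never applies to a listed illness.

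A listed event that should return only through the intended criterion then stays off the SAE page and outside the 24-hour reporting of 8.4.1. It also stays out of the AE and SAE tables of SAP 4.3.2.1, because SAP 6.1.2 makes HIV-associated conditions available only at participant level. AE incidence is a secondary endpoint.

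The second matter is that 10.3.1 covers what appear to be the same events with a shorter list. Its pointer, which should lead to the full list, goes to an unrelated section.

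**Working it through.** The plan gives no figure to reproduce. The check is a cross-reading and a count.

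**Step 1: does part f match any listed illness?** Section 10.8 lists 25 stage-3-defining illnesses, from candidiasis of the bronchi to HIV wasting syndrome. Compared with the wording of part f, 0 of 25 are pregnancy outcomes. Part f could match only a pregnancy outcome linked to one of these illnesses, and 8.4.5 already makes that an SAE.

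**Step 2: compare the two lists of conditions.**

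| Condition returning the event to SAE reporting | 8.4.7 | 10.3.1 |
|---|---|---|
| Qualifies under SAE part f | yes | no |
| Worse than expected for the participant | yes | yes |
| Possibly related to study intervention | yes | yes |
| Death | yes | no |
| Lymphoma or invasive cervical carcinoma | yes | no |

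Section 10.3.1 carries 2 of the 5 conditions, so 5 − 2 = 3 are absent. The missing part f condition is the one that is empty for listed illnesses anyway. The missing death condition matters little, because death is SAE criterion a and 8.4.6 requires the Death eCRF for all deaths. The omission that matters is the mandatory rule for lymphomas and invasive cervical carcinoma. It covers 3 + 1 = 4 of the 25 illnesses: Burkitt's, immunoblastic and primary brain lymphoma, and invasive cervical cancer.

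**Step 3: what does the wrong letter change?** Take a listed illness that is non-fatal, no worse than expected, judged unrelated, and not one of those four, and suppose it leads to hospital admission.

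- As written, no condition applies, so it stays on the HIV-Associated Conditions page.
- If the intended criterion were the judgement item in part h, admission alone would still give no route. The event would return only if the investigator judged that it qualified under that item.
- If the intended criterion were part c, the event would return.

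The effect of the letter therefore depends on the criterion that was meant, and the documents do not identify it.

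**Step 4: is an editing error plausible?** Other references in the same safety sections also miss their targets. Section 8.4.4 sends causality assessment to 10.3.6.6, which concerns updates after eCRF write access is removed; causality is in 10.3.6.3. Section 10.3.6.6 sends the reader to 8.4.3 for the SAE contact, while 8.4.1 and 10.3.6.7 place the contacts in 8.4.8. Section 10.3.1 points to 8.4.9. This supports a stale reference but does not prove one.

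**The case against.** **The exemption is deliberate.** This stands. Section 8.4.7 says that it applies to events that meet the SAE definition. A reader might count the SAE criteria with no return route of their own in 8.4.7 and blame the wrong letter for all of them. The documents do not support that. Most of that effect is the stated design and would remain after the letter was corrected. Part f names congenital anomalies and so overlaps part e. Possible Hy's Law cases must be reported as SAEs in any case (10.3.2 part h and 10.6).

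**Redundancy with 8.4.5 does not prove error.** This is fair. The death condition also repeats an SAE criterion, and read literally the part f condition prevents a clash between 8.4.7 and 8.4.5 for a linked pregnancy outcome. The case for a wrong letter rests more on the mismatch with all 25 listed illnesses. It is a strong inference, not a demonstration.

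**The target may not be part h.** A reader might conclude that f should simply become h. Part h is plausible, but no text says so.

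**Section 10.3.1 does not contradict 8.4.7.** This stands too. It gives two sufficient conditions and does not say that they are the only ones, so a site can comply with both sections. It does not cite 10.8; that it means the same events is inferred from the shared term and near-identical conditions. Part h also names invasive or malignant cancers as examples of events usually considered serious. What remains is an incomplete list whose pointer fails, and which could mislead a site that uses it alone.

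**Conclusion.** The point holds in a limited form. The first return condition in 8.4.7 cites a criterion that matches 0 of the 25 illnesses to which the section applies, so that route is empty for them; the other four conditions work. The effect is confined to listed events that would return only through the intended criterion. Separately, 10.3.1 repeats 2 of the 5 conditions, omits a mandatory rule that covers 4 of the 25 illnesses, and refers to the wrong section.

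The practical size is small. Up to 42 participants are planned, with CD4 counts of at least 200 and follow-up to Day 39. Active CDC Stage 3 disease is excluded, apart from cutaneous Kaposi's sarcoma that needs no systemic therapy. Exempt events are still recorded on the HIV-Associated Conditions page, and 10.3.1 provides routine review by the safety review team. Events judged related return through the third condition in 8.4.7, so the pausing rule for attributable SAEs in 8.3.7 is not undermined. No efficacy result changes.

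The conclusion assumes that the first condition was meant to reach HIV-related illnesses, and that the disease-related events of 10.3.1 are those of 10.8. It is a minor correction, worth making because sites must act on these rules within 24 hours.

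**What to change.** Reconcile 8.4.7, 10.3.1 and 10.3.2 with three sentence-level edits:

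1. The sponsor states which SAE criterion 8.4.7 intends in place of part f.
2. The same list of conditions appears in 8.4.7 and 10.3.1, or 10.3.1 states that 8.4.7 governs.
3. The pointer in 10.3.1 changes from 8.4.9 to 8.4.7.

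These can go into the next protocol amendment or a clarification letter to sites. They add no procedures, visits or staff and leave the SAP analyses unchanged. Which criterion applies is for the sponsor to decide.

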8.4.9. Participant card

The investigator must provide the participant with a “participant card” containing information about the clinical study. The participant must be instructed to always keep the participant card in their possession for the duration of the study. In an emergency, this card serves to inform the responsible attending physician that the participant is in a clinical study and that relevant information may be obtained by contacting the investigator(s) or their back up.

8.5. Pharmacokinetics

- Intensive and single PK sampling is pre-specified as per the SoA (Section 1.3).

CCI

- Otherwise on single PK draw days a single PK sample will be drawn in conjunction with the study visit and as close to an every-24-hour post last dose cycle as possible.
- Collected PK samples may not be analyzed if concentrations below the limit of quantification were previously achieved or if the participant was assigned to placebo.
- Refer to [Table 7](#) for the permissible windows for CCI, dosing and PK draws for intensive PK days.

Table 7 Intensive Pharmacokinetic Sampling Schedule on Day of Dosing

	Time of Event	Window	Time Relative to Dosing Hour:Minute
	CCI		
Dosing Day	Pre-dose PK collection	Not applicable	Collect pre-dose sample prior to dosing. There is allowance to collect the sample earlier and up to 90 minutes prior to dosing
	Administer study treatment and start the clock for subsequent blood draws.	Not applicable	00:00
CCI			

- Instructions for the collection and handling of biological samples will be provided by the sponsor.

- Blood samples of approximately 2 mL will be collected and processed to plasma for measurement of plasma concentrations of study intervention.
- The actual date and time (24-hour clock time) of each sample will be recorded.
- Samples to be stored in an upright position at -70°C or colder until shipment to the test laboratory. Refer to the List of Clinical Laboratories and Key Vendors document for laboratory names and addresses of the clinical laboratories used in this study.
- A maximum of 2 mL samples may be collected at additional timepoints during the study if warranted and agreed upon between the investigator and the sponsor. The timing of sampling may be altered during the study based on newly available data (e.g., to obtain data closer to the time of peak plasma concentrations) to ensure appropriate monitoring.
- Plasma samples will be used to evaluate the PK concentrations of VH4004280 or VH4011499 and may also be used to evaluate safety or efficacy aspects related to concerns arising during or after the study.
- Intervention concentration information that would unblind the study will not be reported to investigative sites or blinded personnel until the study has been unblinded.

8.6. Pharmacodynamics

See Section 8.2 and Section 8.5 for relevant efficacy and PK assessments.

8.7. Genetics of the Participant

A 6 mL blood sample for deoxyribonucleic acid (DNA) isolation will be collected on Day 1 from participants who have consented to participate in the genetic analysis component of the study. Participation is optional. Participants who do not wish to participate in the genetic research may still participate in the study.

In the event of DNA extraction failure, a replacement genetic blood sample may be requested from the participant. Signed informed consent will be required to obtain a replacement sample unless it was included in the original consent.

See Section 10.5 for information regarding genetic research. Details on processes for collection and shipment and destruction of these samples can be found in Laboratory Manual.

8.8. Biomarkers - Viral Genotyping and Phenotyping

Plasma samples for exploratory resistance testing will be collected according to the schedule described in Section 1.3 and as detailed in the Laboratory Manual. Resistance results will not be available in time to inform the treatment management of participants during the study. Samples from Day 1 (pre-dose) and Day 11 will be batch tested for viral genotypic and phenotypic on treatment changes and/or resistance to the CAIs using the

Monogram Biosciences Inc. based assays. Plasma from additional timepoints may be assayed if needed.

Additional blood samples may be drawn for local genotypic/phenotypic analysis, according to local guidelines. These tests are optional and will be conducted in accordance with local guidelines for the management of HIV-1 infection and, if available, may be used to guide the choice of standard of care cART. Locally obtained genotypic/phenotypic results will be retained in the participant's medical record at the site and will not be transferred to VH/GSK.

VH/GSK may store samples for up to 20 years after the end of the study to achieve study objectives. Additionally, with participants' consent, samples may be used for further research by VH/GSK or others such as universities or other companies to contribute to the understanding of HIV-1 or other diseases, the development of related or new treatments, or research methods.

